#### **4.1.2. Exclusion criteria**

*Patients who meet the following exclusion criteria will be excluded from this study*

1. *Patients with a diagnosis of valvular AF (standard disease code: 8846941), postoperative AF (8847772), AF associated with mechanical valve malfunction (T82.0), mechanical complication of heart valve prosthesis (T82.0), or rheumatic AF (I05-I09) during the baseline period\*\*.*
2. *Patients with a diagnosis of VTE during the baseline period*
3. *Patients who are prescribed any anticoagulant during the baseline period.*
4. *Patients who are prescribed anticoagulants other than warfarin and apixaban on the index date*
5. *Patients who were hospitalized for more than 6 months (including index date) regardless of reason for hospitalization.*

*\*\*: maximally 6 months prior to the index date. If sufficient patient information is available for the analysis, patients who cannot have a 6-month baseline period will be included in the analysis.*

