8.1.1.1. Index date

The next day of the day when patients diagnosed NVAF initiate warfarin or apixaban

8.1.1.2. stroke

8.1.1.3. Defined using pre-designated ICD-10 codes (see Statistical Analysis Plan). Ischemic and hemorrhagic stroke will be included,stroke

Stroke is defined using predefined ICD-10 codes and if hospitalization for the treatment of the stroke is necessary, it will be regarded as stroke incident during the followup period.
(applicable only to the outpatients when recurrent stroke occurs)

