8.1.1.6. Baseline period

Period of 180 days before the index date.

8.1.1.7. Follow up period:

The end of observation is the period until the first observation of the earlier of the following items.

1. discontinuation of the index OAC (warfarin or apixaban, OAC prescribed on the index date); the index treatment is considered to be discontinued if there is a continuous gap of 45 days or more between the expected refill date and the actual refill date.
2. switch to another OAC; the index treatment is regarded as switched if the index OAC was discontinued and another OAC was started within 45 days of the prescription refill date of the index OAC.
3. lack of further records in the database; if no further relevant records are added (e.g., no further refills or visits), the last date of the patient's record in the database is considered.
4. occurrence of stroke or major bleeding (endpoints).
5. elapsing of 2 years from the index date.

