8.2.2 Exclusion criteria

Patients who meet the following exclusion criteria will be excluded from this study

- 1 Patients with a diagnosis of valvular AF (standard disease code: 8846941), postoperative AF (8847772), AF associated with mechanical valve malfunction (T82.0), mechanical complication of heart valve prosthesis (T82.0), or rheumatic AF (I05-I09) during the baseline period.
- 2 Patients with a diagnosis of VTE during the baseline period
- 3 Patients who are prescribed any anticoagulants before index date.
- 4 Patients who are prescribed anticoagulants other than warfarin and apixaban on the index date
- 5 Patients who are continuously hospitalized due to the first incidence of stroke or other serious diseases.

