## 5. ENDPOINTS AND COVARIATES

### 5.1. EFFICACY/EFFECTIVENESS ENDPOINT(S)

#### 5.1.1. Primary effectiveness endpoint and primary analyses

The following outcomes will be assessed as effectiveness endpoints. Primary endpoint is incidence of a composite of recurrent stroke (ischemic and hemorrhagic stroke)/SE in NVAF patients treated with warfarin or apixaban. The definition of “recurrent” is as follows, “once patients discharge from the hospital and become outpatients and then rehospitalized due to stroke (major reason for the hospitalization is stroke described in the DPC admission information)

[figure not shown]
[figure not shown]
1. Incidence rate (per 1,000 person-years) of a composite of recurrent stroke (ischemic and hemorrhagic stroke)/SE during the follow-up period in NVAF patients treated with warfarin or apixaban
2. Time course of proportion of the incidence of a composite of recurrent stroke (ischemic and hemorrhagic stroke)/SE-free NVAF patients treated with warfarin or apixaban (shown as two Kaplan-Meier curves, for warfarin cohort and apixaban cohort, which will be statistically compared by a Log-rank test).
3. Risk of a composite of recurrent stroke (ischemic and hemorrhagic stroke)/SE in patients treated with apixaban compared to that in patients treated with warfarin. Hazard ratio and 95% confident intervals will be calculated by a COX proportional hazard method

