## 5.2. SAFETY ENDPOINTS

### 5.2.1. Primary safety endpoint and primary analyses

The following outcomes will be assessed as safety endpoints. The primary safety endpoint is **major bleeding**, which is defined as any bleeding requiring hospitalization for treatment (the primary reason for the hospitalization is to treat the bleeding). Because "hospitalization" is a requirement, only outpatients will be included in the analysis and patients who are already hospitalized at the time of bleeding (bleeding during hospitalization) will be excluded from the analysis.

1. Incidence rate (per 1,000 person-year) of **major bleeding** during the follow-up period in NVAF patients treated with warfarin or apixaban.
2. Time course of proportion of **major bleeding**-free in NVAF patients treated with warfarin or apixaban (shown as two Kaplan-Meier curves, for warfarin cohort and apixaban cohort, which will be statistically compared by a Log-rank test).
3. Risk of **major bleeding** in NVAF patients treated with apixaban compared to that in patients treated with warfarin. Hazard ratio and 95% confident intervals will be calculated by a COX proportional hazard method.

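### Exclusion 5 can select different patients in the protocol and the SAP, and patients who start in hospital accrue time in which no stroke or major bleed can be counted

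*SAP*

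**What the plan says.** **Who is excluded.** Exclusion 5 in Protocol 8.2.2 removes "Patients who are continuously hospitalized due to the first incidence of stroke or other serious diseases". It names reasons and gives neither a duration nor a reference date. Exclusion 5 in SAP 4.1.2 removes "Patients who were hospitalized for more than 6 months (including index date) regardless of reason for hospitalization". It names a duration and sets the reason aside. SAP section 1 lists no amendments, and the SAP does not explain the difference.

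**When follow-up starts and ends.** Protocol 8.1.1.1 defines the index date as "The next day of the day when patients diagnosed NVAF initiate warfarin or apixaban", without requiring the patient to be an outpatient. Protocol 8.1.1.7 ends observation at the latest on "elapsing of 2 years from the index date". Neither document moves the start of risk time to discharge.

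**What counts as a primary event.** SAP 5.1.1 counts a stroke as recurrent "once patients discharge from the hospital and become outpatients and then rehospitalized due to stroke". The stroke definition in Protocol 8.1.1.3 adds that it is "applicable only to the outpatients when recurrent stroke occurs". For major bleeding, SAP 5.2.1 says that "patients who are already hospitalized at the time of bleeding (bleeding during hospitalization) will be excluded from the analysis". No admission rule is stated for systemic embolism, the other component of the primary effectiveness composite.

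**What counts as a secondary bleed.** SAP 5.2.2 counts intracranial, gastrointestinal and intraocular bleeding whether or not the patient is in hospital.

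**The concern.** There are three linked problems.

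First, the cohort for the main comparison is not uniquely defined. Starting an anticoagulant during the qualifying stroke admission is foreseeable here. The SAP's own propensity model has terms for inpatient treatment, length of stay and discharge destination of the most recent stroke. Whether such patients are in or out affects the size and case-mix of the secondary prevention cohort.

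Second, if the six-month stay may be completed after the index date, eligibility depends on what happens after time zero. A patient kept in hospital by a complication could be removed, while one who dies in hospital on day 60 stays in.

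Third, patients who are in hospital at index contribute person-time from index but cannot have a counted stroke or major bleed until discharge. The denominators of the incidence rates, which are a stated objective, then include days that cannot produce a numerator. If those days are unequal between the drugs, the hazard ratio moves as well.

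**Working it through.** **1. The two exclusions side by side**

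| Patient at index | Protocol 8.2.2 | SAP 4.1.2 |
|---|---|---|
| Starts during a 2-month first-stroke admission | can be excluded | kept |
| In hospital 7 months for a reason that is not a serious disease | kept | excluded |

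Neither rule contains the other, so the SAP rule is not simply the protocol rule made operational.

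**2. The reference date of the SAP rule**

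SAP exclusions 1 to 3 are tied to the baseline period, and exclusion 5 is not. Its parenthesis about the index date allows two readings: six months up to and including index, or a stay of more than six months that contains index. Only the second uses post-index information, and the text does not choose.

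**3. The plan's own figures**

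The power table in SAP 7.2.2 reproduces with Schoenfeld events and exponential follow-up over 2 years. For a hazard ratio of 0.6 and 1.2 %/year:

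- events = 4 × (1.960 + 0.842)² / (ln 0.6)² = 120.3
- event probabilities = 1 − exp(−0.024) = 0.0237 and 1 − exp(−0.0144) = 0.0143
- n per group = 120.3 / 0.0380 = 3,166, as stated

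All 12 cells agree within about 1.2%, so the table has no arithmetic error.

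Power is not the main harm. Take 15,000 patients split 1:1 (the split is an assumption), a hazard ratio of 0.65, 1.2 %/year on control and full 2-year follow-up. Power is 95.8% with no hospital time and still 89.4% if every patient had 180 days not at risk.

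**4. Effect on the rates and the ratio**

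The documents give neither the share starting in hospital nor the post-index stay. Assumed values:

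- s = share in hospital at index, the same in both arms: 25%, 50% or 100%
- L = mean post-index stay of those patients: 40 days on warfarin, 20 on apixaban
- F = mean follow-up: 365 days, with 730 (the maximum) for comparison
- true ratio: 0.65, the value expected in SAP 7.2.2

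Reported rate = true rate × (F − sL)/F

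Reported ratio = 0.65 × (F − sL_apixaban)/(F − sL_warfarin)

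The second formula is for the rate ratio, used here as an approximation to the Cox hazard ratio when events are rare.

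| s | Warfarin rate too low (F = 365) | Apixaban rate too low (F = 365) | Reported ratio, F = 365 | Reported ratio, F = 730 |
|---|---|---|---|---|
| 25% | 10/365 = 2.7% | 5/365 = 1.4% | 0.65 × 360/355 = 0.66 | 0.65 × 725/720 = 0.65 |
| 50% | 20/365 = 5.5% | 10/365 = 2.7% | 0.65 × 355/345 = 0.67 | 0.65 × 720/710 = 0.66 |
| 100% | 40/365 = 11.0% | 20/365 = 5.5% | 0.65 × 345/325 = 0.69 | 0.65 × 710/690 = 0.67 |

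With the stays reversed (20 days on warfarin, 40 on apixaban) and F = 365, the ratio reads 0.64, 0.63 and 0.61. With equal stays it stays at 0.65 while both rates remain too low.

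**The case against.** **Weighting should reduce the imbalance.** The propensity score in SAP 7.1.2 includes duration of the most recent stroke admission, its treatment status, functional and consciousness scores at admission, and discharge destination, with balance checked at 0.1. This stands in part: a 40 versus 20 day gap is the kind of imbalance that weighting is meant to shrink. But the covariate is total stay rather than post-index stay, it covers stroke admissions only, and equal stays would not correct the rates.

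**The SAP may only be making the protocol operational.** The protocol wording is loose enough to describe long-stay patients, for whom the SAP supplies a threshold, and Protocol 8.7 leaves detailed methods to the SAP. But Protocol 8.7 defers the analysis methods, not eligibility, and the SAP also drops the reason for the stay.

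**The six months may end at index.** A reader might infer that the SAP rule definitely looks into the future. The documents do not establish that: the footnote to the same list defines its other six-month window as time before index. What stands is that the rule is ambiguous.

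**Inpatients may already be outside the safety analysis.** SAP 5.2.1 says that "only outpatients will be included in the analysis and patients who are already hospitalized at the time of bleeding" are left out. Read broadly, this removes inpatients altogether. But SAP 4.2 uses one analysis set for bleeding and effectiveness, and dropping patients because they bled in hospital would condition on the outcome.

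**The primary endpoints are not wholly closed to inpatients.** A reader might infer that an inpatient can have neither primary endpoint. That holds for stroke and major bleeding; for systemic embolism no such rule is stated.

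**Figures.** The figures beside the definition of recurrence in SAP 5.1.1 are not in the text reviewed. If they show a risk window, the SAP prose should state it.

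**Conclusion.** The point holds. The two exclusions can select different patients, and the reference date of the SAP rule needs stating. As written, the plan counts hospital days after index in which a stroke or major bleed cannot be counted, so both rates per 1,000 person-years are understated. Under the assumptions shown, the understatement is about 1% to 11%.

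Bias in the hazard ratio is conditional: it needs post-index stay to differ by drug after weighting. A reader might infer that the ratio is pulled toward 1, to 0.69 or beyond. The documents do not support that: 0.69 requires every patient to start in hospital and longer stays on warfarin, and neither is documented. At a share of 25% the same stays give 0.66, and with the stays reversed the shift goes the other way.

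This should be settled before the analysis is run. It does not threaten the study's power.

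**What to change.** 1. Write one exclusion 5, identical in both documents, that uses only information up to and including the index date.
2. For the two primary endpoints (stroke/SE and major bleeding), start time at risk at discharge, by delayed entry, for patients in hospital at index. State how a systemic embolism in hospital is counted.
3. Keep time at risk from the index date for intracranial, gastrointestinal and intraocular bleeding. A reader might extend the discharge start to every endpoint at no cost, but SAP 5.2.2 counts these bleeds in inpatients, so that would delete countable events.
4. Report by drug the number starting in hospital, their post-index stay, and exits before discharge.

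The cost is a short amendment to each document and a programming change, using admission and discharge data that the plan already relies on. The downside is small: the primary analyses lose pre-discharge days and the patients who never reach discharge. That last loss is itself a selection after index, which is why item 4 asks for exits before discharge.

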8.2. Setting

8.2.1. Inclusion criteria

Patients must meet all the following selection criteria

1. Patients registered in the MDV database 2008 though 2021.
2. Patients newly with non-valvular atrial fibrillation
3. Patients who newly receive warfarin or apixaban after diagnosis of NVAF
4. Age 20 years or older on the index date
5. Patients who have a history of stroke or TIA are inclusion criteria only for secondary prevention cohort, otherwise patients will be concluded in the primary prevention cohort.

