8.9. Limitations of the research methods

Our study, like most retrospective analyses using claims data, has several intrinsic limitations and certain expected biases.

1. The data we will use is obtained from a claims database containing information provided by hospitals applying the flat-fee payment system, which are mostly large hospitals responsible for acute care. Therefore, a significant proportion of the patients included in the present analysis will be likely in poorer health than the average population requiring hospitalization, possibly having more comorbidities and higher risk of stroke and bleeding.
2. The claims data we will use here do not include vital signs or laboratory data such as blood pressure, international normalized ratio values, and renal function parameters, which is also why we could not calculate a HAS-BLED score. These variables will not be considered in the calculation of the propensity score, and there is no guarantee that such characteristics are fully balanced after s-IPTW. Therefore, although we will compute a propensity score based on multiple variables that may affect the risk of stroke and bleeding, the influence of unexamined confounding factors will not be fully excluded.
3. We will not provide an estimation of follow-up loss, as we will have no subsequent data on patients who visited a different hospital or clinic after being registered with one of the hospitals contributing to the MDV database. This could result in an underestimation of the incidence of stroke or major bleeding events.

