**\*NSAIDs chronic use**

Patients who have been prescribed NSAIDs at least a 90-day during the baseline period. For non-oral drugs, the difference between each prescription day is counted as the number of prescription days.

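### The SAP keeps patients without a full baseline on an undefined sufficiency test, so new-starter status and baseline covariates cannot be verified when the prior record is short

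*SAP*

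**What the plan says.** **Baseline.** Protocol 8.1.1.6 defines it as "Period of 180 days before the index date". The footnote to SAP 4.1.2 makes it "maximally 6 months prior to the index date" and then adds: "If sufficient patient information is available for the analysis, patients who cannot have a 6-month baseline period will be included in the analysis". Neither document says what makes information sufficient. SAP Appendix 1 (data derivation) is marked not applicable. SAP section 6 (missing values) is one sentence that, read literally, removes the patients with complete data, and it does not define sufficiency either. SAP section 1 lists no amendments.

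**Prior anticoagulants.** Protocol 8.2.1 requires "Patients who newly receive warfarin or apixaban after diagnosis of NVAF", and Protocol 8.2.2 excludes "Patients who are prescribed any anticoagulants before index date". SAP 4.1.2 excludes "Patients who are prescribed any anticoagulant during the baseline period", which ties the exclusion to the window that the footnote allows to be short.

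**Covariates.** SAP 7.1.2 reads all the propensity-score medicines, and most of the comorbidities, from baseline. BMI, treatment status of the last stroke, mRS, JCS and ADL have a missing category. Drugs and comorbidities have none. Length of prior record is not a covariate.

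**Checks.** SAP 4.4 lists no subgroups. The only sensitivity analysis, in SAP 7.2.1, is the E-value.

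**The concern.** The comparison is meant to be between patients starting warfarin and patients starting apixaban. Whether someone is a starter is judged from the record before the index date. If that record is short, the absence of an earlier anticoagulant is weak evidence, and the same weakness affects the antiplatelet, NSAID, heparin and comorbidity covariates that build the weights. Continuing users may be patients who have tolerated treatment, or patients whose stroke occurred while on it, so their event rate could be lower or higher than that of true starters. A standardized difference below 0.1 would show balance on recorded values only. An undefined sufficiency test also allows the cohort to be settled after the data have been seen.

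**Working it through.** **1. How a short record passes the SAP criteria.** Stroke history is searched from first appearance in the MDV database to the day before index, with no minimum length (SAP 4.1.1). The index date is the day after the initiating prescription (Protocol 8.1.1.1). In the extreme case, a patient first seen on the prescription day has a one-day look-back and can meet every SAP criterion. A patient whose first record is a stroke admission has only the days from admission to index. Anticoagulant use before the first record is invisible in both.

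The narrower SAP exclusion opens a second, smaller route. SAP 2.1.3 takes the first prescription after NVAF diagnosis, so the recorded use that escapes is use before that diagnosis and more than 6 months before index.

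**2. What happens to covariates.** The SAP does not state a coding rule. With no missing category, however, a drug or disease without a record can only be read as absent. Weighting then balances the recorded value.

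**3. Possible size.** The SAP expects a hazard ratio of about 0.65 (SAP 7.2.2). Let q be the share of hidden continuing users in an arm and r their event rate relative to true starters. Both are assumptions; the documents give neither.

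Observed HR = 0.65 × (1 − q_a + q_a·r_a) / (1 − q_w + q_w·r_w), where a is apixaban and w is warfarin.

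| Assumed case | q = 0.1 | q = 0.3 |
|---|---|---|
| Warfarin only, r = 0.7 | 0.65/0.97 = 0.670 | 0.65/0.91 = 0.714 |
| Warfarin only, r = 1.5 | 0.65/1.05 = 0.619 | 0.65/1.15 = 0.565 |
| Apixaban only, r = 0.7 | 0.65 × 0.97 = 0.6305 | 0.65 × 0.91 = 0.5915 |
| Apixaban only, r = 1.5 | 0.65 × 1.05 = 0.6825 | 0.65 × 1.15 = 0.7475 |
| Both arms, same q and r | 0.65 | 0.65 |

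With a wider warfarin-only range, q from 0.1 to 0.4, the result is 0.66-0.77 for r of 0.6-0.8 and 0.63-0.54 for r of 1.25-1.5.

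**4. Can a restricted analysis be afforded?** First, the plan's own table. Schoenfeld events are 4(1.960 + 0.842)²/ln(HR)². Divide by the sum of the event probabilities 1 − exp(−2·rate) and 1 − exp(−2·rate·HR), with no dropout. The 2-year horizon is inferred from the follow-up cap in Protocol 8.1.1.7. At 1.2 %/year this gives 3,165, 6,113 and 14,756 per group for hazard ratios of 0.6, 0.7 and 0.8, against the stated 3,166, 6,083 and 14,683. All 12 cells agree within 1.2%.

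At HR 0.65 and 1.2 %/year: events = 4 × 7.849/0.1856 ≈ 169.2; probabilities 0.02371 + 0.01548 = 0.03919; 169.2/0.03919 ≈ 4,317 per group, or 8,634 in total. Against the 15,000 patients in SAP 7.2.2, 1 − 8,634/15,000 = 42% could be lost before power falls below 80%.

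| Control rate, %/year | Total for 80% power, 1:1 | Share of 15,000 that could be lost, 1:1 | Same, if 30% are on warfarin (assumption) |
|---|---|---|---|
| 1.2 | 8,634 | 42% | 25% |
| 1.6 | 6,498 | 57% | 44% |
| 2.1 | 4,972 | 67% | 57% |
| 2.6 | 4,033 | 73% | 65% |

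These shares are optimistic. They assume two full years on treatment for everyone and no loss of precision from weighting.

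**The case against.** Several stronger readings are tempting, and the documents do not support them.

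- **That the SAP breaches a required 180 days of record.** Protocol 8.1.1.6 defines a window, and no protocol criterion demands that it be fully observed. The SAP settles a case the protocol left open. The sharper conflict is between the two anticoagulant exclusions.
- **That these patients have an empty baseline.** A secondary-prevention patient must have a stroke or TIA recorded before index, and any diagnoses and drugs entered with it before index count. The baseline is short, not empty.
- **That the 90-day NSAID rule corrupts the weights.** "Patients who have been prescribed NSAIDs at least a 90-day during the baseline period" belongs to the variable table in SAP 5.4. The propensity list in SAP 7.1.2 asks only whether NSAIDs were used in baseline. A single long oral prescription might also meet the rule within a short record.
- **That the protocol already admits the problem.** In Protocol 8.9, "we will have no subsequent data on patients who visited a different hospital or clinic" concerns care after registration, that is, loss to follow-up. Unseen earlier care is a fair inference from a database limited to contributing hospitals, but it is not stated there.
- **That the comparator is mislabelled.** Patients are assigned by the drug actually first prescribed (SAP 2.1.3). Only starter status is in doubt.
- **That the hazard ratio is biased in a known direction.** Either drug may have been started elsewhere, and equal contamination leaves 0.65 unchanged. Every illustrated value still favours apixaban.

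Two further points stand. Keeping patients with short records can be defended on representativeness. Treatment at a non-contributing clinic also stays invisible with 180 or more days of MDV record, so the footnote is not the only cause.

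What survives is an undefined inclusion test, a narrowed exclusion, covariates that depend on an unmeasured look-back, and no analysis that would reveal the effect. An E-value addresses unmeasured confounding, not continuing users admitted as starters.

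**Conclusion.** The concern holds as a risk of unknown size and direction. Following SAP 4.1.2 as written admits patients whose new-starter status cannot be verified and whose baseline drugs and comorbidities are under-recorded, and weighting cannot repair either. The affected share, its difference between arms and the relative event rate are not in the documents. The hazard ratios shown therefore indicate what could happen under assumed, mostly one-sided inputs and are not an estimate of the bias. The plan should be changed before analysis, because the remedy is cheap and on the SAP's own planning figures a restricted analysis looks feasible.

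**What to change.** 1. Delete the sufficiency test. State that patients with a short look-back stay in the main cohort under a rule fixed before data extraction. The simplest rule is that everyone who meets the other criteria is included, whatever the length of record.
2. Derive observed look-back (first MDV record to index) for every patient and add it to the propensity model. One workable grouping is under 30, 30-179, and 180 days or more. Only the 180-day cut comes from the protocol. This balances observation time; it does not recover unrecorded covariates.
3. Pre-specify a repeat of the primary effectiveness and primary safety hazard ratios in patients with at least 180 days of prior record. Report look-back by arm, including the number and share below 180 days.
4. Reconcile exclusion 3 in SAP 4.1.2 with Protocol 8.2.2, so that any anticoagulant recorded before the initiating prescription, over all available look-back, excludes the patient. SAP 4.1.1 already searches stroke history that way. The wording should refer to the initiating prescription: with the index date set one day later, that prescription itself falls before index and, read literally, triggers the exclusion in both documents.

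**Cost.** One derived variable, one propensity term, one further run of two models, and revised text. Steps 1 to 3 do not shrink the main cohort; step 4 may remove some patients with older recorded use. The restricted analysis has fewer patients and wider intervals. It reduces but does not remove bias from treatment at non-contributing clinics, and that should be stated as a limitation.
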